### 3.2 Study Groups

- Intervention group: Patients treated with FlowTriever®
- Comparison group: Patients treated with thrombolysis
- Intervention group with prior thrombolysis: a subgroup of the intervention group including patients that have received thrombolysis before FlowTriever®. They will be separately described and exploratively analyzed as an own intervention group within the study. No formal statistical comparisons will be made for this group.

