## 5.4 Intervention

Following variables related to the intervention of FlowTriever® will be summarized:

- Indication for intervention (e.g. contraindication to thrombolysis, unsuccessful thrombolysis, other indication)
- Contraindication to thrombolysis (none, trauma, surgery, ischemic stroke, hemorrhagic stroke, active bleeding, risk for bleeding, ongoing anticoagulation, other indication)
- Use of Cellsaver/FlowSaver™ or equivalent
- Rescue treatment after intervention (thrombolysis, surgical embolectomy, ECMO)
- ECMO during intervention (yes, no)
- Technical success (yes, no), defined as achievement of desirable catheter positioning, as assessed by the interventionist
- Procedural success (yes, no), defined as technical success with successful extraction of thrombus material in the absence of major complications, as assessed by the interventionist

- Clinical success (yes, no), defined as hemodynamic or respiratory improvement following intervention, including but not limited to: increase in SaO2, reduced FiO2, regress of hypotension/tachycardia/tachypnoea, reduced need for circulatory support.
- Complications during intervention (bleeding, perforation, other complication)
- Other complications (coded by ICD-10 if relevant)

Following variables related to the treatment with thrombolysis will be summarized:

- Dose of thrombolysis
- Duration of infusion of thrombolysis
- Reason for premature discontinuation of thrombolysis (when relevant)
- Contraindication for thrombolysis (if relevant)
- Rescue treatment after thrombolysis (surgical embolectomy, ECMO)

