### 5.5.2 Secondary Outcome Variables

The secondary variables in this study are:

- Difference in RV/LV-ratio as compared (up to 48h) before, and (up to 48h) after, treatment. RV/LV-ratio before treatment will be assessed on CT, and after treatment on echocardiography.
- Difference in pulmonary artery pressure (systolic, diastolic and mean) as compared (up to 48h) before and (up to 48h) after treatment.
- Incidence of severe bleeding (according to GUSTO bleeding criteria) within 7 days after treatment
- Type of bleeding (severe, moderate, mild GUSTO)
- Intracranial bleeding (yes, no)
- Incidence of all-cause death at 30 days after treatment
- Time to all-cause death within 30 days after treatment
- Causes of death in patients treated with FlowTriever® vs thrombolysis
- Occurrence of cardiac arrest before (within 24 hours), during, or after (within 24 hours) treatment
- Occurrence of rescue treatment with thrombolysis, ECMO, or surgical thrombectomy
- Length of stay in ICU or IMU (hours)
- Length of hospital admission (days)

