### 6.2 General Methodology

Descriptive statistics will be used for group characteristics and outcomes. Mean, standard deviation, median, and range will be described for the continuous variables and frequency and percentage for categorical variables. Intergroup comparisons considering baseline characteristics will be done using Fisher's exact test for

dichotomous variables, Chi-square test for non-ordered categorical variables, and the Mann-Whitney U-test for continuous variables.

The comparative analyses between the groups considering the dichotomous study outcomes will be performed using logistic regression adjusted for known and statistically identified confounders (variables that are related both to the study group and the outcome). Odds-ratios (OR) with associated 95% CI, p-values and area under the receiver operating characteristic curve (AUC-ROC) will be presented. Hosmer-Lemeshow test will be performed as a goodness-of-fit test.

The comparative analyses between the groups considering the continuous study outcomes will be performed using linear regression adjusted for known and statistically identified confounders. Model assumptions will be checked by reviewing diagnostic plots, and if needed transformation (e.g. log) of the outcome variable will be performed. Least square means with associated 95% CI, p-values and  $R^2$  will be presented.

Outcome variables length of stay in ICU (hours) and length of hospital admission (days) will be handled as continuous variables in the case of no censored patients. In case of censored patients in the database, time to discharge will be studied using Cox proportional hazard model, resulting in hazard ratios (HR) with 95% CI and p-value. Proportional hazards assumptions will be checked graphically. Otherwise, the variables will be studied as continuous variables using either linear regression assuming normal distribution if applicable or Poisson or negative binomial regression depending on the distribution of the variables. Results from the Poisson and negative binomial regression result in risk ratio (RR) with 95% CI and p-value.

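### The exploratory rescue-treatment outcome counts thrombolysis after FlowTriever but not FlowTriever after thrombolysis, so its between-group comparison is biased against FlowTriever whenever the second sequence occurs

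*SAP*

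**What the plan says.** Section 5.5.2 of the SAP lists as one secondary outcome "Occurrence of rescue treatment with thrombolysis, ECMO, or surgical thrombectomy". FlowTriever and other catheter treatments are not among the components.

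Section 5.4 sets out what is collected in each group. For FlowTriever patients it is "Rescue treatment after intervention (thrombolysis, surgical embolectomy, ECMO"); for thrombolysis patients it is "Rescue treatment after thrombolysis (surgical embolectomy, ECMO").

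The SAP foresees FlowTriever after thrombolysis. Section 5.4 records "Indication for intervention (e.g. contraindication to thrombolysis, unsuccessful thrombolysis, other indication"), and section 5.6 lists an inadequate earlier response to thrombolysis as a candidate confounder. Section 3.2 defines "a subgroup of the intervention group including patients that have received thrombolysis before FlowTriever", to be described separately, and adds: "No formal statistical comparisons will be made for this group".

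On analysis, section 6.2 states: "The comparative analyses between the groups considering the dichotomous study outcomes will be performed using logistic regression adjusted for known and statistically identified confounders". Section 6.6 applies the general methodology to the secondary outcomes. Rescue is not among the four confirmatory outcomes in section 6.2, so it is tested in an exploratory way at 0.05.

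**The concern.** Escalation from one study treatment to the other can go in two directions. Under sections 5.4 and 5.5.2 only one direction is an event. A FlowTriever patient who then receives thrombolysis adds to the FlowTriever rescue count. A thrombolysis patient who then receives FlowTriever adds nothing to the thrombolysis count and, under section 3.2, also leaves the thrombolysis denominator.

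The recorded thrombolysis rescue rate is therefore too low by construction if any patient follows the second sequence. Covariate adjustment or propensity matching cannot recover events that the definition does not count. At stake is the reading of one exploratory odds ratio: a difference against FlowTriever could be produced, or a difference in its favour hidden, by the definition alone.

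**Working it through.** **The SAP's own figures.** No figure in the SAP concerns rescue. Its only power statement is for the primary composite (section 6.1: 20% against 40%, 60 against 200 patients, two-sided Fisher's exact test, alpha 0.05, at least 80% power). Exact enumeration gives 82.7%, so that statement reproduces. It has no bearing on this point.

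**Events by sequence of treatment.**

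| Sequence | Group under section 3.2 | Rescue event under 5.4 and 5.5.2? |
|---|---|---|
| FlowTriever, then thrombolysis | FlowTriever | Yes |
| Thrombolysis, then FlowTriever | FlowTriever (subgroup) | No |
| Either treatment, then ECMO or surgery | As treated | Yes |

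If a reader instead kept the second row in the thrombolysis group, those patients would still be non-events, because FlowTriever is not a listed component.

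**Illustration 1: thrombolysis rescue rate.** Input from the SAP: 200 thrombolysis patients (section 6.1). Assumed, because the SAP does not give them: 10 ECMO or surgical rescues among the 200, and k = 6 to 15 patients with thrombolysis then FlowTriever. Recorded rate: 10/200 = 5.0%. Symmetric rate: (10 + k)/(200 + k).

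- k = 6: 16/206 = 7.8%
- k = 9: 19/209 = 9.1%
- k = 12: 22/212 = 10.4%
- k = 15: 25/215 = 11.6%

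Relative understatement: 1 − 5.0/7.8 = 36% to 1 − 5.0/11.6 = 57%. The odds move from 10/190 to (10 + k)/190, so the unadjusted odds ratio, FlowTriever against thrombolysis, is multiplied by (10 + k)/10 = 1.6 to 2.5.

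**Does the subgroup in the FlowTriever denominator offset this?** Section 3.2 leaves it unclear whether the k patients enter the formal FlowTriever group. If they do, and none has a later rescue, they dilute the FlowTriever rate by (60 − k)/60, taking the 60 from section 6.1. The recorded risk ratio divided by the symmetric one is then (60 − k)/60 × [(10 + k)/(200 + k)]/0.05.

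- k = 6: 0.90 × 1.55 = 1.40
- k = 15: 0.75 × 2.33 = 1.74

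On these inputs the net direction is still against FlowTriever. With x recorded thrombolysis rescues in place of 10, the two effects balance when 200(60 − k)(x + k) = 60x(200 + k). That gives x = 41.5 (20.8% of 200) at k = 6 and x = 34.6 (17.3%) at k = 15. Only above such rates could this dilution outweigh the missing events.

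**Illustration 2: no true difference.** Assume 5% ECMO or surgery in both groups, the same crossover proportion c in both directions, and 60 against 200 patients. Recorded rates are 5% + c for FlowTriever and 5% for thrombolysis. The chance of p < 0.05 is from an unadjusted Fisher's test, not the planned adjusted model.

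| c | Recorded rates | Spurious odds ratio | Chance of p < 0.05 |
|---|---|---|---|
| 2% | 7% v 5% | (0.07/0.93)/(0.05/0.95) = 1.43 | 7.6% |
| 5% | 10% v 5% | (0.10/0.90)/(0.05/0.95) = 2.11 | 24.5% |
| 10% | 15% v 5% | (0.15/0.85)/(0.05/0.95) = 3.35 | 63.8% |

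With crossover counted in both groups the odds ratio is 1 and the chance of p < 0.05 is 3% to 4%.

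**The case against.** The omission can be seen as a consequence of the grouping. Once anyone who had FlowTriever is in the intervention group, listing FlowTriever as rescue after thrombolysis would capture nobody. That explains the gap in section 5.4 but does not repair the comparison: the failed thrombolysis courses are still missing from the thrombolysis count.

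Crossover will also be visible. The subgroup is described separately without formal testing, and the FlowTriever indication is recorded. This stands, and it makes the fix cheap, but it does not put the events into the planned odds ratio.

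Equal crossover in both directions is doubtful, since contraindication to thrombolysis is a named reason for FlowTriever and later thrombolysis may then be uncommon. This weakens the false-positive chances in Illustration 2. It does not remove the distortion. The recorded odds ratio exceeds the symmetric one by the ratio of true to recorded thrombolysis odds, whatever the FlowTriever crossover rate. If no FlowTriever patient crossed over and c = 10% of thrombolysis patients did, the recorded odds ratio would be 1.00 where the symmetric one is (0.05/0.95)/(0.15/0.85) = 0.30.

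A reader might infer more than the SAP supports:

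- That rescue is the SAP's measure of treatment failure. It is never called that; it is one of twelve secondary items, and FlowTriever success is defined separately in section 5.4.
- That every control could have been escalated to FlowTriever. Section 3.1 opens inclusion at the start of the calendar year in which a centre introduced the device, so some controls may predate it.
- That a sizeable crossover group is expected. Section 3.2 gives no number.
- That the whole comparison is uninterpretable. ECMO and surgical embolectomy are collected in both groups and can be compared by component.

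**Conclusion.** The point holds for one exploratory secondary outcome. Sections 5.4 and 5.5.2 count crossover in one direction only, and section 3.2 takes the uncounted patients out of the thrombolysis group. The counting rule biases the rescue comparison against FlowTriever whenever a thrombolysis patient goes on to FlowTriever. If the prior-thrombolysis subgroup is kept in the formal FlowTriever group, dilution may offset part of this; on the inputs assumed here it does not reverse the direction.

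The size cannot be obtained from the SAP. The shift from 5.0% to between 7.8% and 11.6% rests on an assumed 10 rescues among 200 patients and an assumed 6 to 15 crossovers, and its relative size depends on that low base.

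It would be wrong to carry this over to the main results. The primary composite, the other three confirmatory outcomes, the Bonferroni-Holm family and the sample size do not use the rescue definition. Whether grouping by treatment received affects those outcomes is a separate question.

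**What to change.** Reconcile sections 3.2, 5.4 and 5.5.2 by one of two routes.

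1. Define rescue in the same way for both groups: any further reperfusion treatment (thrombolysis, FlowTriever or other catheter intervention, surgical embolectomy) or ECMO, started after the first reperfusion treatment. For this outcome only, group patients by the first reperfusion treatment received, so that thrombolysis followed by FlowTriever is an event in the thrombolysis group.
2. Restrict the between-group comparison to ECMO and surgical embolectomy, and report crossover in both directions descriptively, by component.

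Both are changes of SAP wording. The crossover patients are already identified through sections 3.2 and 5.4.

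Route 1 costs more than a footnote. The groups for this outcome differ from those for all other outcomes. The FlowTriever denominator shrinks by k (60 − 15 = 45 at the upper assumed value). The covariate for inadequate earlier response to thrombolysis cannot be used as an adjuster in this model. Route 2 avoids these costs but gives up a single rescue composite. Either way only the counting of an outcome changes, not care.

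### Hospital and ICU/IMU length of stay have no stated start point, so time before treatment can enter the exploratory group comparison

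*SAP*

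**What the plan says.** Section 5.5.2 of the SAP names two stay outcomes: "Length of hospital admission (days" and "Length of stay in ICU or IMU (hours". Neither entry has a start point. Several neighbours in the same list do, for example "Time to all-cause death within 30 days after treatment".

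Section 6.2 gives the analysis. Without censoring, "Outcome variables length of stay in ICU (hours) and length of hospital admission (days) will be handled as continuous variables", by linear, Poisson or negative binomial regression. With censored patients, "time to discharge will be studied using Cox proportional hazard model". No time zero is given for either branch.

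Section 5.4 describes how patients come to FlowTriever: "Indication for intervention (e.g. contraindication to thrombolysis, unsuccessful thrombolysis, other indication". The recorded reasons are "Contraindication to thrombolysis (none, trauma, surgery, ischemic stroke, hemorrhagic stroke, active bleeding, risk for bleeding, ongoing anticoagulation, other indication". The same section also records contraindications in the thrombolysis group where relevant.

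Contraindication is a candidate confounder in section 5.6, but only the strongest candidates enter the adjusted models. Section 5.3 records hours from diagnostic radiology to treatment. No listed variable records time from hospital admission to treatment. Sections 6.2 and 6.3 place the stay outcomes outside the Bonferroni-Holm set.

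**The concern.** Time that passed before treatment cannot be an effect of treatment. If stay is counted from admission, a patient who develops PE on day 8 of a surgical admission brings about a week of earlier stay into the outcome. A patient treated on arrival brings almost none. When the groups differ in how many patients were already in hospital, the comparison of stay partly reflects where patients were when the PE occurred, and only partly recovery after treatment.

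The Cox branch has the same problem in another form. With admission as time zero, the interval up to treatment is time at risk of discharge before exposure. Nobody in the cohort can be discharged in it, because everyone had to remain in hospital long enough to be treated. This is immortal time.

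An undefined start also leaves each centre free to take a different date from the records. At stake is the interpretation of two secondary outcomes that will be tested at the 0.05 level.

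**Working it through.** **The plan's own figures.** The SAP gives no figure for length of stay, so there is none to reproduce. From section 6.1 only the group sizes are used: 60 FlowTriever and 200 thrombolysis patients.

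**Step 1: does the text set a start point?** Section 5.5.2 gives none for either stay outcome, and section 6.2 gives models only. The ordinary meaning of the hospital item is admission to discharge, and nothing in the SAP overrides it. The ICU/IMU item is open.

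**Step 2: can pre-treatment time differ by group?** Trauma, surgery, stroke and active bleeding can each go with an earlier admission, and contraindication is a named indication for FlowTriever. A difference is therefore plausible. The SAP does not report how many patients in either group were in hospital before the PE.

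**Step 3: spurious difference in mean stay, with no treatment effect.** Let pF and pT be the shares already in hospital (FlowTriever, thrombolysis) and m their mean pre-treatment days, taken as equal in both groups. Then

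spurious difference = (pF − pT) × m

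All inputs below are assumptions.

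| pF | pT | m (days) | Calculation | Difference (days) |
|---|---|---|---|---|
| 20% | 5% | 5 | 0.15 × 5 | 0.75 |
| 30% | 5% | 7 | 0.25 × 7 | 1.75 |
| 40% | 10% | 10 | 0.30 × 10 | 3.0 |

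If the shares were reversed, the sign would reverse: (0.05 − 0.20) × 5 = −0.75 days.

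**Step 4: effect on a test at 0.05.** A simulation of 2,000 runs used 60 vs 200 patients and no treatment effect. Post-treatment stay was log-normal in both groups (median 7 days, SD 0.8 on the log scale), and pre-treatment days were exponential with mean m. The test was an unadjusted t-test on log stay. These distributions are also assumptions.

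| pF vs pT | m (days) | Mean shift (days) | Rejections, counted from treatment | Rejections, counted from admission |
|---|---|---|---|---|
| 20% vs 5% | 7 | 0.15 × 7 = 1.05 | 4.3% | 13.3% |
| 30% vs 10% | 7 | 0.20 × 7 = 1.4 | 4.3% | 19.5% |
| 50% vs 10% | 7 | 0.40 × 7 = 2.8 | 5.6% | 58.0% |
| 50% vs 10% | 14 | 0.40 × 14 = 5.6 | 5.0% | 85.7% |

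The last two rows use a wider gap in shares than step 3 and show the far end of the range. Counting from treatment removes the shift by construction, and the rejection rate stays near the nominal 5%.

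**Step 5: would the planned adjustment remove it?** Only in part. Contraindication may or may not be selected. If it is, it balances categories, not days: within the surgery category, for example, some patients are still in hospital and others have gone home. Section 6.2 limits the propensity score analyses to the four confirmatory outcomes, which do not include stay. Table 5.1 in section 7 could be read as extending them to all secondary outcomes, but the variable list in section 5.6 still has no measure of pre-treatment time.

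**The case against.** The strongest reply is that this is a missing definition and not a decision to count pre-treatment days. Other entries in section 5.5.2, such as type of bleeding, intracranial bleeding and rescue treatment, also lack an anchor, so brevity is the style of the list. The definition may also sit in a protocol that is not at hand. This stands in part: the SAP nowhere says that the clock starts at admission. But it does specify the models for these outcomes, including a time-to-event model, and such a model cannot be fitted without a time zero.

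A reader might also infer that the plan will show a longer stay with FlowTriever even when recovery is identical. The document does not support that. It does not say that many FlowTriever patients were already in hospital, or that thrombolysis patients came through the emergency department. Some contraindications, such as ongoing anticoagulation, imply no earlier admission, and trauma or surgery may belong to an admission that had ended. Thrombolysis patients may also be inpatients.

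Finally, contraindication could well be selected for these models. With 60 + 200 = 260 patients, most of whom would have a discharge event, the limit of one variable per 10 events allows up to about 26 variables and is unlikely to bind. This mitigation is real, but it is neither guaranteed nor complete, and it does not supply a time origin.

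**Conclusion.** The point holds as a gap in definition with a plausible route to bias. Neither stay outcome is anchored to treatment, the literal reading of the hospital item includes pre-treatment days, and the Cox model has no time zero.

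Size and direction are unknown. The range of about 0.75 to 3 days is unadjusted and rests on three assumptions: admission is the start point, the excess share of inpatients in the FlowTriever group is 15 to 30 percentage points, and their mean earlier stay is 5 to 10 days. The immortal-time problem arises only if the Cox branch is used and admission is time zero.

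The consequence is confined to two exploratory outcomes. The primary outcome and the other three outcomes in the Bonferroni-Holm set are not touched.

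**What to change.** In sections 5.5.2 and 6.2:

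- Define hospital stay as days from the start of the index treatment to hospital discharge, and ICU/IMU stay as hours from the start of the index treatment to ICU/IMU discharge.
- State which treatment start counts for patients who had thrombolysis before FlowTriever, since section 3.2 keeps them within the intervention group.
- Use the same start as time zero in the Cox model for discharge.
- Report pre-treatment time in hospital by group in Table 1.1. Total admission length may be kept as a description, without a between-group test.

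The cost is a few lines of SAP text and one row in Table 1.1. Treatment times are already needed for the 7-day and 30-day outcomes and discharge times for stay. The admission date comes from the same patient records.

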## 5.6 Confounders and Predictors

The confounders and predictors for the outcomes will be used in propensity scores and adjustments. All variables listed below will be included when building propensity scores. For the adjusted analyses, only the

strongest confounders and predictors will be part of the analyses. The number of confounders/predictors in the adjusted analyses will be based on the number of events available in the studied cohort. The general recommendation is to not have more than 1 variable/10 events in a statistical model. We will calculate the maximum number of variables in our study as N events/10.

The following variables will be investigated whether they are statistically defined confounders, i.e. related to both the intervention and the outcome:

- Contraindication for thrombolysis (8 categories)
- Insufficient previous effect of thrombolysis
- Cardiac arrest before treatment

The following variables will be investigated for their relation to the study outcomes:

- Age
- Sex
- Active cancer
- Invasive ventilation before treatment
- Circulatory instability
- Chronic heart failure
- Chronic pulmonary disease (COPD, asthma, other)
- Respiratory rate >30 beats/min
- Center

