## 4 Study Populations

### 4.1 Full Analysis Set

The full analysis set (FAS) will include all patients treated with FlowTriever® and thrombolysis at the included centers during the years 2021, 2022 and 2023.

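### SAP 5.6 makes failed prior thrombolysis a mandatory propensity-score covariate although only FlowTriever patients can have it, and the SAP does not say whether those patients are in the comparison

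*SAP*

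**What the plan says.** Section 5.6 sets two rules. For the propensity score there is no selection: "All variables listed below will be included when building propensity scores". For the outcome models only the strongest variables enter, up to a maximum of events divided by ten, counted in variables. Three variables, among them "Insufficient previous effect of thrombolysis" and contraindication (given there as 8 categories), "will be investigated whether they are statistically defined confounders, i.e. related to both the intervention and the outcome".

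Three other sections bear on who can have the covariate and who is compared:

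- Section 3.2 describes prior thrombolysis only within the FlowTriever arm, as "a subgroup of the intervention group including patients that have received thrombolysis before" the device. It adds: "No formal statistical comparisons will be made for this group".
- Section 4.1 makes no such exception: "The full analysis set (FAS) will include all patients treated with" either therapy at the centres in the study years.
- Section 5.4 lists failed thrombolysis among the FlowTriever variables ("Indication for intervention (e.g. contraindication to thrombolysis, unsuccessful thrombolysis, other indication"). For the comparison group it lists "Rescue treatment after thrombolysis (surgical embolectomy, ECMO", with no second course of thrombolysis.

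Sections 6.2 and 6.5 use the score twice, as an adjustment covariate and for 1:1 matching. The caliper is 0.2 SD of the logit, and matching counts only if at least 70% of FlowTriever patients find a match.

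**The concern.** Comparison patients are defined by thrombolysis as their study treatment, so they have no earlier failed course to record. A covariate that is positive in one arm only predicts treatment perfectly wherever it is positive. A logistic propensity model then has no finite coefficient for it.

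The same item can enter the primary regression. There it acts as a switch: an indicator that is positive only among treated patients absorbs their outcomes, so they no longer contribute to the treatment odds ratio. Since 5.6 picks confounders partly by association with the outcome, the data could settle which population the primary result describes. In a non-randomised comparison that should be settled in advance.

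A smaller issue lies in the same section. A cap counted in variables charges one unit for contraindication, which needs seven or eight coefficients.

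**Working it through.** **Inputs from SAP 6.1:** 60 FlowTriever and 200 thrombolysis patients; composite risk 20% versus 40%; two-sided Fisher's exact test at 0.05. **Assumed, because the SAP gives no figure:** 10-20% of FlowTriever patients (6 or 12 of the 60) have failed prior thrombolysis, with a composite risk of 20%, 40% or 60%.

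**1. The plan's own figure.** Exact enumeration of Fisher power for 60 versus 200 at 20% versus 40% gives 82.7%. The stated minimum of 80% reproduces.

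**2. Propensity score, patients kept.** With 6 or 12 positives among 60 FlowTriever patients and none among 200 controls, Newton fits gave a coefficient of about 7.5 after 5 iterations, 12.5 after 10 and 22.5 after 20, with no limit. The fitted score for these patients goes to 1, so no control is within reach. They use 6-12 of the 18 unmatched places that the 70% rule allows (0.7 × 60 = 42 must match).

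The indicator's own contribution to the caliper is 0.2 × √(p(1−p)) × coefficient:

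- p = 6/260: 0.030 per unit, so 0.030 × 7.5 = 0.23 after 5 iterations and 0.030 × 22.5 = 0.68 after 20.
- p = 12/260: 0.042 per unit, so 0.32 rising to 0.95.

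The match tolerance for all other patients therefore depends on a software stopping rule.

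**3. Propensity score, patients excluded.** The covariate is 0 for everyone. It has no estimable coefficient, and the instruction to include it cannot be carried out.

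**4. Primary odds ratio.** The control odds are 0.40/0.60 = 0.667.

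- Excluded, or indicator in the model: (0.20/0.80)/0.667 = 0.375.
- Kept without the indicator, 20% risk: unchanged at 0.375.
- Kept, 40% risk: the FlowTriever risk is (54 × 0.20 + 6 × 0.40)/60 = 0.22, odds ratio 0.42; with 12 such patients 0.24 and 0.47.
- Kept, 60% risk: 0.24 and 0.47 with 6 patients; 0.28 and 0.58 with 12.

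In 1,500 simulated cohorts per scenario with two further covariates, the log odds ratio with the indicator in the model matched that after exclusion (median absolute difference 0.002-0.005). Under an assumed selection rule of p<0.05 against the outcome, the indicator was picked in 1-31% of runs.

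**5. Power under each choice** (exact Fisher, 200 controls, these patients assumed to come out of the 60):

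| Choice | 6 patients | 12 patients |
|---|---|---|
| Excluded (54 or 48 left) | 78.4% | 75.4% |
| Kept, their risk 20% | 82.7% | 82.7% |
| Kept, their risk 40% | 73% | 61% |
| Kept, their risk 60% | 61% | 37% |

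**6. The cap.** Expected events are 0.2 × 60 + 0.4 × 200 = 92, so the cap is 9. Section 5.4 lists nine contraindication levels including none, hence 8 parameters, or 7 if none is one of the 8 categories in 5.6. Ten events per parameter is already lost at 10 parameters (92/10 = 9.2), reached when two or three single-parameter variables join contraindication. The upper bound, nine variables without centre, is 15-16 parameters, or 92/16 = 5.8 to 92/15 = 6.1 events each. For severe bleeding at an assumed 5-15% there are 13-39 events and a cap of 1-3. Contraindication alone then leaves 13/8 = 1.6 to 39/7 = 5.6 events per parameter.

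**The case against.** The strongest reply is that the separated score does little harm. Leaving patients without a counterpart unmatched is what a caliper is for, and the plan reports it through the drop-out analysis and the 70% rule. In simulations with 6 or 12 such patients, four assumed covariates and 250 cohorts per setting, the score entered as a probability gave a median log odds ratio within about 0.02 of the analysis excluding these patients. Matching came within about 0.06 and yielded 47-54 pairs, above the 42 needed. Drift was visible only when the score entered as a linear logit (about -0.66 to -0.97, against -0.89 to -1.05); section 6.5 does not fix that scale. This stands: separation mostly acts as exclusion, and only sensitivity analyses are affected.

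A reader might therefore infer too much in three ways. One is that both propensity-score analyses rest on a separated score; that is true only if the patients are kept, which the SAP leaves open. Another is that the primary regression separates too; it does not, because the indicator there is related to the outcome rather than used to predict treatment. The third is that section 3.2 already excludes these patients; its sentence can equally be read as covering only the separate description of the subgroup, and 4.1 keeps them.

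It can also be said that a control might receive repeat thrombolysis after a failed first course. The SAP does not define the covariate that way, and 5.4 lists no such rescue for that group.

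Finally, deleting the item alone could make matters worse. With the patients kept, deletion moved the score-adjusted log odds ratio from about -0.95 to as far as -0.5 in the same simulations. This stands and determines the order of the fix. On the cap, the rule as written can be met and 5.6 calls it a general recommendation, so that part is minor.

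**Conclusion.** The inconsistency is certain: the mandatory covariate fails under either reading, by separation or by being constant, and sections 3.2, 4.1 and 5.6 do not settle which reading holds. The consequence is conditional. The primary odds ratio moves from 0.375 to 0.42-0.58 only if these patients are kept, the indicator is not selected, and their risk is 40-60% rather than 20%; the share and the risks are assumptions. The effect on the propensity-score analyses may be small. What should not remain is a confirmatory population that outcome data could choose. Counting the cap in variables is a lesser fault: it does not preserve the events-per-parameter ratio it is meant to protect. The sample-size statement itself is correct for 60 versus 200. The sponsor should make the change before analysis.

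**What to change.** Treat steps 1 and 2 as one package.

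1. Before analysis, reconcile 3.2, 4.1 and 5.6 by stating whether patients with thrombolysis before FlowTriever enter the confirmatory comparison. Report the other choice as a sensitivity analysis. If they are excluded, restate the power for the reduced group.
2. With the population fixed, remove the failed-thrombolysis item from the propensity score and from the outcome-model candidates. Do not delete it without step 1.
3. Minor: count the events/10 cap in covariate parameters, separately for each binary outcome, and pre-specify any collapsing of the contraindication categories.

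The cost is SAP wording, small programming changes and one extra sensitivity analysis on data already to be collected. The downsides are somewhat lower stated power if these patients are excluded, possible dilution of the effect if they are kept, and some residual confounding where categories are collapsed.
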